8.4.6 Adverse events of special interest

An AE of special interest is any AE that a regulatory authority has mandated be reported on an expedited basis, regardless of the seriousness, expectedness, or relatedness of the AE to the administration of a UCB product/compound. No AEs of special interest have been identified for PSL to date, with the exception of potential Hy's Law as described below.

Potential Hy's Law, defined as $\geq 3 \times \text{ULN}$ ALT or AST with coexisting $\geq 2 \times \text{ULN}$ total bilirubin in the absence of $\geq 2 \times \text{ULN}$ ALP, with no alternative explanation for the biochemical abnormality, must ALWAYS be reported to UCB as an AE of special interest (ie, without waiting for any additional etiologic investigations to be concluded). Follow-up information should then be reported if an alternative etiology is identified during investigation and monitoring of the study participant.

8.5 Safety signal detection

Selected data from this study will be reviewed periodically to detect, as early as possible, any safety concern(s) related to the study medication so that Investigators, study participants, regulatory authorities, and IRBs/IECs can be informed appropriately.

The Study Physician or medically qualified designee/equivalent will conduct an ongoing review of SAEs and perform ongoing SAE reconciliations in collaboration with the UCB PS representative.

As appropriate for the stage of development and accumulated experience with the study medication, medically qualified personnel at UCB may identify additional safety measures (eg, AEs, vital signs, laboratory or ECG results) for which data will be periodically reviewed during the course of the study.

8.6 Efficacy assessments

Not applicable.

8.7 Treatment of overdose

For this study, any dose of PSL greater than that prescribed in the protocol will be considered an overdose. Overdose events are only considered AEs or SAEs if there are associated clinical signs and/or symptoms or if the act of taking the excess study medication itself is an AE or SAE (eg, suicide attempt).

UCB does not recommend specific treatment for an overdose. Padsevonil will not be self-administered by the study participant.

In the event of an overdose, the Investigator should:

1. Contact the UCB Study Physician immediately.
2. Closely monitor the study participant for any AE/SAE and laboratory abnormalities until study medication can no longer be detected systemically (at least 3 days).
3. Obtain a plasma sample for PK analysis within 3 days from the date of the last dose of study medication if requested by the UCB Study Physician (determined on a case-by-case basis).
4. Document the quantity of the excess dose, as well as the duration of the overdose, in the eCRF.

Decisions regarding dose interruptions will be made by the Investigator in consultation with the UCB Study Physician based on the clinical evaluation of the study participant.

8.8 Genetics

Archived blood samples for genotyping of drug metabolizing enzymes and/or transporters will be collected as specified in the Schedule of Activities.

8.9 Biomarkers

Not applicable.

8.10 Samples for PSL bioanalytical method cross-validation

Mitra™ and venous blood samples will be collected as specified in the Schedule of Activities. The bioanalytical results from these samples will not be reported in the clinical study report. They will be included in the bioanalytical cross validation report.

9 STATISTICAL CONSIDERATIONS

A description of statistical methods follows and will be described in more detail in the Statistical Analysis Plan (SAP). Deviations in analyses from the final SAP will be documented in the clinical study report.

9.1 Definition of analysis sets

The following are the defined analysis sets:

- Enrolled Set (ES): All study participants who have signed the ICF.

- Safety Set (SS): All study participants who received at least one dose of study medication.
- Pharmacokinetic Per Protocol Set (PK-PPS): the PK-PPS is a subset of the SS, consisting of those study participants who had no important protocol deviations affecting the PK of EE, LN, or PSL and its metabolites and for whom at least one measurable concentration exists.

9.2 General statistical considerations

Statistical evaluation will be performed by the Sponsor or designee and supervised by the Early Development Statistics Department of UCB. All statistical analyses will be performed using SAS[®] Version 9.4 or later (SAS Institute, Cary, NC, USA).

For continuous variables, summary statistics will include number of study participants, mean, median, standard deviation, minimum, and maximum (geometric mean and geometric coefficient of variation [CV] for plasma concentrations and PK parameters). Categorical endpoints will be summarized using number of study participants, frequency, and percentages. Missing data will not be imputed. Individual plasma concentration and PK parameters will be presented using three significant digits.

If not otherwise stated, Baseline will be the last assessment prior to dosing. Measurement of specific Baseline values will be described in the SAP.

9.3 Planned pharmacokinetic analyses

All PK analyses will be performed using the PK-PPS. Pharmacokinetic parameters of EE, LN, PSL, and PSL metabolites (eg, C_{max} , t_{max} , AUC or AUC_{0-t} or AUC_{τ} , $t_{1/2}$ or CL/F) will be estimated using noncompartmental analysis with Pharsight Phoenix[®] WinNonlin[®] v6.3 (or higher) software. Pharmacokinetic analyses will be performed and reported for each study part (Part 1 and Part 2).

The individual time-plasma concentrations of EE, LN, PSL, PSL metabolites, and PK parameters of EE, LN, PSL and PSL metabolites will be summarized by treatment using descriptive statistics (number of observations, geometric mean, lower and upper 95% confidence intervals [CI], geometric coefficient of variation [CV], arithmetic mean, standard deviation [SD] and CV, median, and minimum and maximum value) and graphical displays.

Ethinylestradiol/levonorgestrel primary PK parameters will be compared between treatments using analysis of variance for a cross-over design (treatment, period, sequence as fixed effects, and subject within sequence as random effect) on the log-transformed parameters and estimation of the geometric mean ratio of PK parameters between groups with their 90% CI will be provided.

Lack of PSL effect on EE/LN will be concluded if the 90% CI of the geometric mean ratio between treatment PSL+EE/LN and treatment EE/LN of the least squares means for the log-transformed AUC, and C_{max} is within the bioequivalence acceptance range of 80% to 125%.

If the 90% CI is slightly broader than the BE criteria, individual AUC and C_{max} geometric means ratios will be assessed with the aim of achieving >0.7 (less than a 30% decrease OC exposure in the presence of PSL) to declare a lack of a clinically significant PK interaction.

Pharmacokinetic parameters ($C_{max,ss}$, AUC_{τ}) of PSL and its metabolites will be compared between days with OC [Part 1: Day 13 for Treatment Sequence A and Day 30 for Treatment

Sequence B; Part 2: Day 9 for Treatment Sequence A and Day 26 for Treatment Sequence B] and without OC [Part 1: Day 12 for Treatment Sequence A and Day 29 for Treatment Sequence B; Part 2: Day 8 for Treatment Sequence A and Day 25 for Treatment Sequence B] using analysis of variance on the log-transformed parameters and estimation of geometric ratio of PK parameters between days with their 90% CI will be provided.

The relationship between individual AUC ratio (with and without PSL) of EE and LN, and the exposure to PSL (AUC_{τ}) will be assessed by scatterplots and linear regression analyses (log-transformed and also untransformed data).

The estimated slope with 95% CI will be computed. In absence of interaction, intercept and slope will be equal to 0.

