Section 9.3, Planned pharmacokinetic analyses	-Specified that PK analyses will be performed and reported for each study part. -The criteria for lack of clinically significant interaction between PSL and OC have been further specified. -Study days for which PK parameters will be compared have been specified for Part 2.	-This is necessitated by the addition of Part 2. -This is to allow more flexibility in the interpretation the clinical significance of the PK interaction. -This is necessitated by the addition of Part 2, which does not match Part 1 in terms of treatment days (due to shortening of PSL treatment duration).
Section 9.4, Planned safety analyses	-Specified that safety variables will be listed and summarized by study part. -Specified that safety variables will be listed and summarized for PSL treatment alone, ie, prior to administration of OC in the PSL+OC Period.	-This is necessitated by the addition of Part 2. -This was not previously specified.
Section 9.9, Determination of sample size	This has been revised to account for discontinuation of Part 1 before the planned 20 study participants were enrolled and to describe the power	This was necessitated by the addition of Part 2.

Section # and Name	Description of Change	Brief Rationale
	associated with the planned 26 study participants in Part 2.	
Section 10.2, Appendix 2: Clinical Laboratory Tests and Section 10.4.2.2, Pregnancy testing	Revised to reflect that all pregnancy tests in the study are serum pregnancy tests rather than urine pregnancy tests.	Clarifications to the nonapplicable text of standard protocol template appendices.
Section 10.10, Appendix 10: Abbreviations and trademarks	New abbreviations have been added.	Standard procedure.

ALP=alkaline phosphatase; ALT=alanine aminotransferase; AST=aspartate aminotransferase; BID=twice daily; C-SSRS=Columbia Suicide Severity Rating Scale; EDV=Early Discontinuation Visit; EOS=End of Study; h=hour(s); OC=oral contraceptive; PK=pharmacokinetic; PSL=padsevonil; QTc=QT interval corrected for heart rate; SFU=Safety Follow-up; TM=registered trade mark; VAT=value added tax

This document cannot be used to support any marketing authorization application and any extensions or variations thereof.

REDACTED COPY

SERIOUS ADVERSE EVENT REPORTING

Serious adverse event reporting (24h)	
Fax	Europe and Rest of the World: [contact]
Email	Global: [contact]

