1.1.5 Overall design

This is a Phase 1, open label, randomized, 2-way cross-over study to investigate the potential pharmacokinetic (PK) interaction of PSL with OC in healthy female study participants.

Prior to Protocol Amendment 2, the intention was to screen a sufficient number of study participants to ensure that 20 study participants would be included in each treatment sequence shown in Table 1-2. This pair of treatment sequences has now been designated as Part 1, necessitated by the introduction of a new pair of treatment sequences at the new, lower

dose level, termed Part 2, for new study participants that will be enrolled under the amended protocol. At the time of Amendment 2, 14 study participants completed Part 1 and were dosed with PSL 400mg BID (7 study participants in Sequence A and 7 study participants in Sequence B). In Part 2, a sufficient number of study participants will be screened to ensure that 13 study participants are included in each treatment sequence.

Each Part of the study (1 and 2) consists of a Screening Visit, 2 Treatment Periods with at least a 14-day washout between periods, and a Safety Follow-up (SFU) Visit that will occur no sooner than 7 days, and at a maximum of 10 days (Part 1) or 14 days (Part 2) following the final dose of study medication.

Study participants who provide written informed consent will be screened during the 28-day period from Day -29 to Day -2. Study participants who meet all inclusion and none of the exclusion criteria will check into the clinic on Day -1 (Baseline, the day prior to Day 1, the first day of the first Treatment Period, and will be randomized into one of the 2 treatment sequences: Treatment Sequence A or Treatment Sequence B (see Section 1.3, Schedules of activities).

Each study participant will be dosed with OC and OC+PSL during the 2 Treatment Periods in either Treatment Sequence A or Treatment Sequence B. If the study participant is randomized to Treatment Sequence A, they will receive OC+PSL during the first Treatment Period followed by OC alone during second Treatment Period. If the study participant is randomized to Treatment Sequence B, they will receive OC alone during the first Treatment Period followed by OC+PSL during the second Treatment Period. There will be a Washout Period of at least 14 days between treatments within each sequence (see Section 1.2, Schema).

Part 1

Sequence A

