2 INTRODUCTION

2.1 Study rationale

Padsevonil is a novel chemical entity with selective affinity for both presynaptic vesicle protein 2 (SV2) isoforms and postsynaptic central benzodiazepine receptor cBZR sites on the GABA_A receptor that has shown compelling, broad-range efficacy in several preclinical models of epilepsy conducted by UCB. Padsevonil is currently being investigated for the treatment of focal onset seizures in adult patients with treatment-resistant epilepsy. Preclinical investigations (NCD2151, NCD2356), which used cryopreserved human hepatocytes, showed that PSL was a weak CYP3A4 inducer. These in vitro findings were confirmed in the clinical DDI study with midazolam, a sensitive CYP3A4 probe substrate (UP0013). Indeed, this study showed that PSL given at 400mg BID reduced the oral exposure of midazolam by 44%.

Oral contraceptives, usually in the form of fixed combinations of estrogen and progestin steroids, are metabolized via oxidation by CYP3A4 at the gut and hepatic level (Zhang et al, 2018). Strong CYP3A4 inducers like rifampin, carbamazepine, and phenytoin, which have very large impact on oral midazolam exposure (>80% exposure reduction), reduced the exposure of EE to a lesser extent (38% to 66%) (Backman et al, 1996). The smaller effect size of EE compared with oral midazolam to CYP3A4 inducers is most likely due to the multiple elimination pathways of EE which may be less inducible than CYP3A4. As a weak inducer of CYP3A4, it is expected that the effect of PSL on EE exposure will be less than that observed for oral midazolam. A fit-for-purpose physiologically-based PK model aiming at predicting the DDI between PSL and EE showed that a weak DDI (16% decrease of EE AUC) may occur at a PSL dose of 400mg BID.

Therefore, UP0035 aims to evaluate the impact of coadministration of PSL on the exposure of EE and LN. The outcome of this study will be used to inform labeling regarding the use of PSL in combination with OC.

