6.3 Measures to minimize bias: randomization and blinding

This study is an open-label study; therefore, no study personnel or study participants will be blinded.

A contract research organization (CRO; ie, ICON) randomization biostatistician will create the program to generate the randomization code. A dummy randomization schedule will be prepared by the randomization biostatistician (a cross-over 2x2 scheme with 2 treatment sequences) and reviewed by the Clinical Study Biostatistician in order to ensure that the code meets the study requirements.

After finalization of the dummy code, the randomization program will be run with a different seed number to create the final randomization list; the final list will be generated and will be

reviewed by a quality control randomization biostatistician. The treatment assignment will be random.

Copies of the randomization lists will be sent before the start of the study in a secure fashion directly from the contracted CRO to:

- Sponsor Patient Safety staff for SAE reporting
- Bioanalytical staff (to identify samples to be measured)
- A member of pharmacy involved in IMP preparation and dispensing
- The Clinical Study Biostatistician/Statistical Programmer

In addition, staff involved in the analysis of PK data, such as a representative from the UCB Clinical Pharmacology/Modeling and Simulation team and a monitor, will have access to the data during the study.

Once the Investigator determines that the study participant is eligible for the study, and before IMP administration, a central person in charge of issuing the randomization numbers will manually allocate a randomization number to the study participant and communicate the randomization assignment to the Site Pharmacist. Each specific randomization number will be linked to the treatment allocation on the randomization schedule, which will be dispensed by the site pharmacist. The randomization numbers will also be recorded in the eCRF.

Each study participant will receive a 5-digit study participant number, from a range of numbers supplied by UCB Clinical Data Operations, Technology, and Standards, assigned at Screening that will serve as the study participant identifier throughout the study. The study participant number will be required in all communication between the Investigator/designee.

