9.9 Determination of sample size

Lack of PK interaction in this study will be concluded if 90% confidence intervals for both AUC and C_{max} geometric means ratios (with/without PSL) of LN and EE are included in the 80% to 125% bioequivalence range.

In a previous OC interaction study conducted by UCB with brivaracetam (N01282), an intra-subject coefficient of variation of 10% for AUC_t for both EE and LN (including C_{max}) and 16% for C_{max} was observed for EE.

Provided that the ratio of the expected means for test (with PSL) and reference (without PSL) is included in the range [0.90, 1.10] and for a type-I error of 0.05 and an intra-subject coefficient of variation of 16%, a total sample size of 34 study participants should allow at least 90% power for the assessment of lack of interaction (or 26 study participants for 80% power).

A total of 40 study participants will be randomized: Part 1 (PSL 400mg BID) will include 14 study participants and will allow a good estimate of the different ratios of PK parameters. Part 2 (PSL 200mg BID) will include 26 study participants (13 study participants in each sequence). Assuming no drop-outs, a decrease of 10% in PK parameters of OC and intrasubject coefficient of variation of 16%, this will allow 80% power for assessing lack of PK interaction.

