## 9.1 Analysis of the primary pharmacokinetic variables

The primary PK variables in plasma used for EE and LN are  $C_{max}$  and AUC.  $C_{max}$  and AUC will be determined from the observed concentration and time data. AUC will be computed using the linear up/log down trapezoidal rule.

The PK individual time plasma concentrations and the primary PK parameters of EE and LN will be summarized by treatment (PSL+OC/OC alone), using descriptive statistics (number of available observations [n], arithmetic mean, median, standard deviation, minimum, maximum, geometric mean, geometric CV and 95% CI for the geometric mean [assuming log-normally distributed data]). Values below the LLOQ will be reported with a clear sign (flag variable in the dataset) indicating that they were below the LLOQ.

Individual study participant concentration-time profiles of EE and LN will be displayed graphically on both linear and semi-logarithmic scales. Spaghetti plots will be presented for all study participants per treatment (OC alone and PSL+OC) and analyte with all study participants overlaid on the same plot (linear and semi-logarithmic scale). Ping-pong plots will also be produced for  $C_{max}$  and AUC for EE and LN (with and without PSL).

The EE/LN primary PK parameters will be compared between treatments (PSL + OC and OC alone) using analysis of variance for a cross-over design (treatment, period, sequence as fixed effects, and subject within sequence as random effect) on the log-transformed parameters and estimation of the geometric mean ratio of PK parameters between treatments with their 90% CI will be provided.

A lack of PSL effect on EE/LN will be concluded if the 90% CI of the geometric mean ratio between treatment PSL+OC and treatment OC alone of the least squares means for the log-transformed AUC, and  $C_{max}$  is within the bioequivalence acceptance range of 80% to 125%.

If the 90% CI is slightly broader than the bioequivalence criteria, individual AUC and  $C_{max}$  geometric mean ratios will be assessed with the aim of achieving  $>0.7$  (less than a 30% decrease in OC exposure in the presence of PSL) to declare a lack of a clinically significant PK interaction.

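### For Part 1, the >0.7 fallback for declaring no clinically significant interaction is post hoc and loosely defined, so it should be descriptive only

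*Protocol*

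**What the plan says.** **Primary rule.** Protocol 9.3 and SAP 9.1 conclude that padsevonil has no effect on EE/LN if the 90% CIs of the geometric mean ratios (GMRs) for AUC and Cmax fall within 80–125%. Protocol 9.9 and SAP 2.3 give this as the only criterion: "Lack of PK interaction in this study will be concluded if 90% confidence intervals for both AUC and" Cmax lie in that range. Protocol 4.2 also says bioequivalence limits define the clinical relevance of the interaction.

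**Fallback.** Protocol 9.3 continues: "If the 90% CI is slightly broader than the BE criteria, individual AUC and" Cmax ratios are to be assessed against 0.7 in order to declare that no clinically significant interaction exists. SAP 9.1 repeats it ("If the 90% CI is slightly broader than the bioequivalence criteria, individual AUC and" Cmax). Neither text limits the fallback to Part 2.

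**Timing.** The Amendment 2 summary of changes says the Section 9.3 criteria for lack of a clinically significant interaction were specified further, and gives the reason: "This is to allow more flexibility in the interpretation the clinical significance of the PK interaction". Protocol 1.1.5 records that "At the time of Amendment 2, 14 study participants completed Part 1". SAP Section 1 dates Amendment 2 to 25 Feb 2020. It adds that the epilepsy project was ended, that nobody will enter Part 2, and that reporting is confined to Part 1.

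**Access.** The study is open-label. Under Protocol 6.3, staff who analyse PK data "will have access to the data during the study".

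**The concern.** A success criterion protects against a favourable reading only if it is fixed before the data exist. Here the criterion was loosened after the last Part 1 completer had finished, and Part 1 is now the only dataset it can be applied to. That makes it post hoc for Part 1 whether or not anyone had seen a concentration.

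The fallback also leaves two choices open. No limit is set on how far outside 80–125% a CI may fall and still count as *slightly broader*. And the ratios to be compared with 0.7 could be one per participant or one GMR per analyte and parameter. Both choices could be made once the results are known.

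At stake is whether a Part 1 result that misses 80–125% is publicly reported as showing no clinically significant interaction with a contraceptive.

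**Working it through.** **Inputs**
- Limits 0.80 and 1.25, one-sided alpha 0.05, planning CV 16%, ratio 0.90, N = 26 or 34: Protocol 9.9.
- Within-subject CV 10% for AUC of EE and LN, 16% for Cmax of EE: Protocol 9.9.
- Part 1 N = 14: Protocol 1.1.5. All 14 are assumed to be in the PK analysis set.
- Predicted effect at the Part 1 dose: Protocol 2.1 says "a weak DDI (16% decrease of EE AUC) may occur at a PSL dose of 400mg BID", a ratio of 0.84. CV 10% is the documented value for that parameter, so CV 16% is a sensitivity value.

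**Formulas** (2×2 crossover, log scale)
- s = √ln(1+CV²); SE = s·√(2/N); df = N−2.
- The CI rule is met when both one-sided t-tests at 0.05 reject. The probability is obtained by integrating over the distribution of the variance estimate.

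**The plan's own figures.** At ratio 0.90 and CV 16%, the smallest even N is 26 for 80% power (exact 0.829) and 34 for 90% (exact 0.911). Both stated sizes reproduce.

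**Part 1, N = 14, df = 12, t = 1.782**
- CV 10%: s = 0.0998, SE = 0.0377, half-width 1.782 × 0.0377 = 0.0672.
- CV 16%: s = 0.1590, SE = 0.0601, half-width 0.1071.
- Expected 90% CI at 0.84: 0.84·exp(±0.0672) = 0.785–0.898; 0.84·exp(±0.1071) = 0.755–0.935. Both lower limits fall a little below 0.80, where the fallback would be invoked.

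**Meeting the >0.7 condition at a true ratio of 0.84**, where ln(0.84/0.70) = 0.1823:
- *Point GMR above 0.7:* z = 0.1823/0.0377 = 4.84 and 0.1823/0.0601 = 3.03.
- *All 14 individual ratios above 0.7:* the SD of one log ratio is s√2 = 0.1411 or 0.2248, assuming the same true ratio in everyone and no period effect. Then z = 1.292 or 0.811, the single-participant probability is 0.902 or 0.791, and its 14th power is 0.236 or 0.038.

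| Condition, true ratio 0.84 | CV 10% | CV 16% |
|---|---|---|
| 90% CI within 80–125% | 34% | 19% |
| All 14 individual ratios >0.7 | 24% | 4% |
| Point GMR >0.7 | >99.9% | 99.9% |

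The last two rows are not conditioned on the CI being only slightly too wide. The point-GMR row is therefore an upper bound on use of the fallback.

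**With a limit on the gate.** Assume *slightly broader* means a lower 90% limit of at least 0.75, with the upper limit still within 1.25, and take the point-GMR reading. A lower limit of 0.75 already implies a GMR above 0.7, so the combined rule reduces to this gate.

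| True ratio | Rule | CV 10% | CV 16% |
|---|---|---|---|
| 0.80 | 80–125% | 5% | 5% |
| 0.80 | 80–125% or fallback | 49% | 26% |
| 0.84 | 80–125% | 34% | 19% |
| 0.84 | 80–125% or fallback | 88% | 55% |

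All figures are for one analyte and one parameter.

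**The case against.** **Origin of the text.** The log prints neither the 0.7 threshold nor the previous Section 9.3, so its addition by Amendment 2 is inferred. This stands as a caveat. The inference is strong, because the fallback is the only part of Section 9.3 that loosens the criterion.

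**Data access.** A reader might infer that the rule was written in the light of Part 1 results. The documents do not support this. Protocol 6.3 permits access to data in general terms and does not mention EE/LN concentrations. Nothing shows they had been assayed or viewed, no interim analysis was planned, and the amendment's stated overall rationale is adverse-event burden and withdrawals.

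**Effect on the conclusion.** A reader might also infer that the fallback reverses the expected Part 1 conclusion. That requires the point-GMR reading and ignores the gate. SAP 9.2 uses individual AUC ratios in a per-participant sense. If all 14 must exceed 0.7, the condition is met less often than 80–125% itself. Only the spread across readings is established.

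**A different margin.** The fallback makes a weaker claim with a wider margin, so passing at a true ratio of 0.80 need not be an error on its own terms. That is fair, but Protocol 4.2 ties clinical relevance to the bioequivalence limits, and the 5% is measured against those.

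**Stakes and power.** The project was terminated, which weakens the labelling argument, and the GMR and 90% CI will be reported anyway. Part 1 claims no power, only a good estimate of the ratios. At ratio 0.90 and CV 16% its power is 0.58, so missing 80–125% cannot be read as showing an interaction. Both points stand and shape the fix.

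**Conclusion.** The concern holds for Part 1. A rule that can turn a missed 80–125% assessment into a declaration of no clinically significant interaction was, on a strong inference, introduced after the Part 1 participants had completed. It now applies to no other data.

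Its effect cannot be given as one number. At n=14 and a true ratio of 0.84, the >0.7 condition is met anywhere from 24% (CV 10%) or 4% (CV 16%) of the time to over 99%, depending on the reading. If the gate is a lower limit of 0.75, which is an assumption, the chance of a favourable declaration at a true ratio of 0.80 rises from 5% to 49% (CV 10%) or 26% (CV 16%). These figures rest on the documented CVs, a log-normal 2×2 model and all 14 participants being evaluable.

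The finding is about pre-specification and definition. It does not show that anyone acted on data, nor which way Part 1 came out. The practical stake is an accurate public record.

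**What to change.** - In SAP 9.1, and listed in SAP 3.9, state that for Part 1 a lack of interaction may be declared only under the 80–125% rule. If that rule is not met, report the GMRs and 90% CIs as estimates and declare neither an interaction nor its absence, because Part 1 claims no power.
- Present any comparison with 0.7 for Part 1 as post hoc and descriptive, beside the 90% CI, and say whether it uses per-participant ratios or GMRs.
- State in the CSR when Part 1 EE/LN concentrations became available, and to which roles, relative to 25 Feb 2020.

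The cost is wording, with no new data or analysis. Before database lock, SAP Section 1 requires a SAP amendment for a changed analysis definition. After lock, the departure would be documented in the CSR, as Protocol Section 9 provides. The downside is a less favourable headline if the CI falls just below 80%.
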